11.1.2 Patient Characteristics

Patient characteristics including demographics and pretreatment characteristics, breast mass and axillary lymph node size, staging evaluation at baseline, medical history, and family history will be summarized. Descriptive statistics including sample size, mean, standard deviation, median, and minimum and maximum values will be presented for continuous variables. Frequency distributions will be presented for categorical variables.

11.1.3 Patient Disposition

Patient disposition including the number of patients enrolled, completed, and discontinued from the study will be summarized overall and by study site. The reasons for discontinuation will also be summarized, and patients who discontinued will be listed.

11.2 HYPOTHESIS AND ENDPOINTS

The hypothesis of this proof of concept pilot trial is that administration of LY3023414 and prexasertib will inhibit NHEJ in metastatic TNBC.

This is an exploratory and descriptive clinical trial in which the primary objective is to assess the objective response rate associated with LY3023414 and prexasertib in metastatic triple negative breast cancer patients.

The secondary objectives of this trial are to assess the duration of response; assess the metastatic TNBC tissues for homologous recombination proficiency and deficiency; and assess expression of phosphorylated proteins involved in homologous recombination.

11.3 SAMPLE SIZE

Ten patients will be enrolled over 12-18 months.

11.4 STATISTICAL METHODS

Ten patients with metTNBC will be enrolled on study and will be treated with LY3023414 and prexasertib. If 0-1 of 10 patients has an objective response to treatment, enrollment will be stopped. If at least 2 of 10 patients has an objective response with treatment, an additional 10 patients could be enrolled on study, following discussion and agreement with Lilly. Expanding the number of patients to 20 would require a protocol amendment. With a sample size of 20 patients, there is an 60% chance of observing 4 or more responses if the true response rate is at least 20%. The complete response rate and duration of response will also be assessed to determine if the combination of LY3023414 and prexasertib will produce exceptional responses of at least 12 months in duration.

A 30% or greater rate of durable (at least 12 months) complete or partial responses would be of high clinical interest and would justify further development of this therapeutic strategy.

PART II – PROCEDURES

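### The 60% chance of 4 or more responses in 20 patients ignores the stop rule at 10: at a 20% true rate the rule gives at most 49% from the start, or 78% given expansion

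*Combined protocol and SAP*

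**What the plan says.** Sections 4.1 and 11.3 plan for ten patients: "Ten patients will be enrolled over 12-18 months".

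Section 11.4 then sets a rule at ten: "If 0-1 of 10 patients has an objective response to treatment, enrollment will be stopped". With two or more responses, "an additional 10 patients could be enrolled on study, following discussion and agreement with Lilly". This step is not automatic: "Expanding the number of patients to 20 would require a protocol amendment".

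The next sentence gives the only probability in the statistical section. For a sample of 20, "there is an 60% chance of observing 4 or more responses if the true response rate is at least 20" percent. It does not say whether the figure sets the stop rule aside, applies from the start of the trial, or applies once expansion has happened. No success rule, null rate or significance level is attached to 4 of 20. The probability of stopping at ten is not stated.

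**The concern.** The rule at ten and the 60% stand in the same paragraph, but they belong to different designs. A fixed-sample calculation for 20 patients includes sequences with 0 or 1 response in the first ten and enough responses in the second ten to reach four. Under the stated rule those sequences cannot occur, because enrollment has already ended.

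A reader can take the 60% in two ways: as the chance, judged before the trial, of reaching 20 patients with 4 or more responses, or as the chance of 4 or more once the trial has grown to 20. If it fits neither, the section's only operating characteristic misdescribes the design. The ethics board and the company, who would have to approve an expansion, would then lack the correct figure and also the chance of stopping early.

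**Working it through.** **Inputs, all from Section 11.4.** First group n = 10; stop at 0–1 responses; possible second group of 10; threshold of 4 responses in 20; true rate p = 0.20, the lower end of the stated range. Let X1 and X2 be the responses in the first and second ten, independent and each binomial(10, p).

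**1. The plan's own figure.** P(X ≥ 4 | n = 20, p = 0.20) = 0.5886, or 58.9%. The stated 60% is therefore the fixed-sample value, rounded.

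**2. Paths that the stop rule removes.**

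P(X1=0)·P(X2≥4) + P(X1=1)·P(X2≥3) = 0.1074 × 0.1209 + 0.2684 × 0.3222 = 0.0130 + 0.0865 = 0.0995.

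**3. From the start, under the rule.** 0.5886 − 0.0995 = 0.4891, or 48.9%. A simulation of 4 million trials gave 0.4890. This is an upper bound, because expansion is optional. If expansion followed only 75% or 50% of the time when allowed (assumed values, independent of the response count), the probability of enrolling all 20 and seeing 4 or more would be 0.75 × 0.4891 = 36.7% or 0.50 × 0.4891 = 24.5%.

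**4. Stopping at ten.** P(X1 ≤ 1) = 0.1074 + 0.2684 = 0.3758, or 37.6%. Hence P(X1 ≥ 2) = 0.6242.

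**5. Given expansion.** If expansion always follows 2 or more responses: 0.4891 / 0.6242 = 0.7835, or 78.4% before rounding of the inputs. By first-group count:

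- exactly 2: P(X2 ≥ 2) = 62.4%
- exactly 3: P(X2 ≥ 1) = 89.3%
- 4 or more: 100%

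If the decision to expand depends on the count in some other way, the result is a weighted average of these three values. It cannot fall below 62.4%.

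**6. Does the wording about 20% or more help?** Both probabilities rise with the true rate, so their minimum values over that range are the 48.9% and 78.4% above. The from-the-start bound reaches 60% only at a true rate of 22.9%. The probability given expansion already reaches 60% at about 14.6%.

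**7. Other true rates**, assuming expansion always follows 2 or more responses:

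| True rate | Fixed 20 | From the start (upper bound) | Given expansion | Stop at 10 |
|---|---|---|---|---|
| 10% | 13.3% | 10.1% | 38.4% | 73.6% |
| 15% | 35.2% | 28.0% | 61.4% | 54.4% |
| 20% | 58.9% | 48.9% | 78.4% | 37.6% |
| 25% | 77.5% | 67.3% | 89.0% | 24.4% |
| 30% | 89.3% | 80.8% | 95.0% | 14.9% |

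The 25% row corresponds to the partial response rate in TNBC quoted in Section 1.5. It is illustrative only: that rate comes from a dose-escalation study whose recommended prexasertib dose differs from this trial's starting dose.

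**The case against.** The strongest reply is that the sentence is correct as written. It opens by fixing the sample at 20, the fixed-sample binomial is 58.9%, and the documents never call the design two-stage or present 60% as a probability from the start. Twenty patients are also not the current plan: stopping at ten only ends the trial at its planned size, and a fuller set of probabilities could wait for the amendment that expansion requires. If 60% is read as a lower bound given expansion, it is conservative rather than false. Finally, the replacement figures assume that expansion always follows 2 or more responses, which the text does not promise.

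Much of this stands. The arithmetic is sound as a fixed-sample calculation, and the 49% and 78% do depend on the expansion assumption, so they must be stated with it. The practical effect is small: Section 11.2 says "This is an exploratory and descriptive clinical trial", and the criterion for further development is a different one: "A 30% or greater rate of durable (at least 12 months) complete or partial responses would be of high clinical interest".

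It does not rescue the figure. Under this paragraph a sample of 20 exists only if at least 2 of the first 10 responded. Taken literally as a condition, the opening words therefore point to the value given expansion and not to 60%. The sentence follows directly on the stop rule and does not say that the rule is set aside. A lower bound 18 points under the value given expansion is not a useful description of the design, and on the from-the-start reading the figure is too high.

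**Conclusion.** The concern holds. The stated 60% is the fixed-sample value and matches neither probability that the stop rule can produce at a 20% true rate. It is about 11 points above the from-the-start bound (60 − 48.9) and about 18 points below the value given expansion (78.4 − 60). The 37.6% chance of stopping a treatment with a 20% response rate at ten patients is missing.

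The results assume independent patients with a common response rate. The 48.9% is an upper bound whatever the expansion decision; the 78.4% assumes that the decision depends on the first ten only through the threshold of 2. This is an error in describing the design and worth correcting, but it affects no test, decision or planned patient number.

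**What to change.** In Section 11.4, keep the sentence but label the figure: *for a fixed sample of 20, not taking account of the stop rule at 10, the probability is 59% at a true rate of 20%.*

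Then add: *With the stop rule, and if expansion always follows 2 or more responses, the probability of enrolling 20 patients and observing 4 or more responses is 49% at a 20% true rate (78% given expansion); the probability of stopping at 10 is 38% at a 20% rate and 74% at a 10% rate.*

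The cost is one label and one sentence. No patients are added, and the stop rule, the analysis and every decision stay as they are. The only drawback is that the from-the-start figure is less favourable than the one now printed. If the text is not revised sooner, the change should be made at the latest in the amendment that an expansion would need.

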12 ADVERSE EVENTS AND SERIOUS ADVERSE EVENTS

All AEs, regardless of severity, will be followed up by the Investigator until resolution is satisfactory. All AEs will be recorded for up to 30 days following the last study treatment.

12.1 **DEFINITIONS**

12.1.1 Adverse Event

An adverse event (AE) is any untoward medical occurrence in a patient or clinical investigation subject, administered a pharmaceutical product and which does not necessarily have to have a causal relationship with this treatment.

An adverse event can therefore be any unfavorable and unintended sign (including an abnormal laboratory finding, for example), symptom, or disease temporally associated with the use of a medicinal product, whether or not considered related to the medicinal product.

12.1.2 Serious Adverse Event

A serious adverse event (experience) or reaction is any untoward medical occurrence that at any dose:

- Results in death,
 - (NOTE: Any death from any cause while a patient is receiving treatment on this protocol, or ≤ 30 days following the last dose of protocol treatment must be reported.)
- Is life-threatening,
- (NOTE: The term "life-threatening" in the definition of "serious" refers to an event in which the patient was at risk of death at the time of the event; it does not refer to an event which hypothetically might have caused death if it were more severe.)
- Requires inpatient hospitalization or prolongation of existing hospitalization,
 - (NOTE: Hospitalization is considered an overnight stay, therefore visits to hospital, without admission, are not considered serious unless they meet another criterion, (eg, medically significant). Planned surgery, or planned admission for study drug, is not considered an SAE unless, the hospitalization is prolonged or if another criterion is met.)
- Results in persistent or significant disability/incapacity, or
- Is a congenital anomaly/birth defect
- Additionally, important medical events that may not be immediately life threatening or result in death or hospitalization, but that may jeopardize the patient or may require intervention to prevent one of the other outcomes listed in the definition above.
 - Examples of such events are intensive treatment in an emergency room or at home for allergic bronchospasm; blood dyscrasias or convulsions that do not result in hospitalization; or development of drug dependency or drug abuse.

12.1.3 Unexpected Adverse Event

An adverse reaction, the nature or severity of which is not consistent with the applicable product information (eg, Investigator's Brochure for an unapproved investigational medicinal product).

12.2 REPORTING

12.2.1 Adverse Events

Adverse events will be recorded for the duration of a patient's study treatment, and for up to 30 days following the last study treatment. All AEs, regardless of causal relationship are to be recorded in the source documentation. Only those specified in Section 9.1 are to be recorded in the CRF. The Investigator will attempt to establish a diagnosis of the event based on signs, symptoms, and/or other clinical information. The diagnosis should be documented as the AE/SAE and not the individual signs /symptoms.

Toxicities will be graded according to the NCI Common Terminology Criteria for Adverse Events (CTCAE) Version 4.0 as linked in Appendix I. The event, and the relationship of each event to treatment, will be assessed by the Investigator and recorded on the CRF. Additional information about each event, such as treatment required, whether or not therapy had to be interrupted or dosages reduced, and eventual outcome will also be recorded on the CRF.

Pre-existing conditions will be recorded at baseline on the Medical History Form. If a pre-existing condition does not change, it does not have to be reported as an AE on **subsequent** cycles.

12.2.2 Serious Adverse Event

All SAEs will be reported per Baylor standard operating procedure (SOP) within 24 hours of becoming aware of the event. All SAEs will be reported by completing a SAE Report Form and emailing the form to the PI. Baylor IRB will be notified via iRIS.

SAEs will be reported to Lilly as soon as possible and no later than 1 business day of the Investigator and/or Institution receiving notification of any serious adverse event experienced by a patient participating in the study and receiving study drug. The preferred method of SAE reporting is via the Lilly Investigator Initiated Research (IIR) portal:

https://www.lillyinvestigatorresearch.com

However, fax is also acceptable to report SAEs to the local safety representative using the following:

Local [contact]

Local [contact]

All SAEs must be documented on the Serious Adverse Event Report Form and on the adverse event CRF page. The event term used on the SAE report should match the term in the CRF.

Follow-up information for SAEs and information on non-serious AEs that become serious should also be reported to the as soon as it is available. For unexpected fatal, life-threatening, or other unexpected SAEs, follow-up information must be reported per Baylor SOP.

12.2.3 Discontinuation of Patient

Discontinuation of a patient on study for the occurrence of a serious or unexpected AE associated with the use of the study medication should be reported to the PI and Project Manager.

12.3 PREGNANCY

Patients of child-bearing potential participating must agree to use one highly effective (less than 1% failure rate) method of contraception or use a combination of two effective methods of contraception during treatment with study drug and for at least 12 weeks following the last dose of study drug.

Note: Unless not allowed by local regulations, patients of child-bearing potential who are abstinent (if this is complete abstinence, as their preferred and usual lifestyle) or in a same sex relationship (as part of their preferred and usual lifestyle) must agree to either remain abstinent or stay in a same sex relationship. Periodic abstinence (eg, calendar, ovulation, symptothermal, postovulation methods), declaration of abstinence just for the duration of a trial, and withdrawal are not acceptable methods of contraception.

Women of child-bearing potential participating must test negative for pregnancy prior to initiation of treatment as indicated by a negative pregnancy test at the screening visit (prior to biopsy) and within 24 hours prior of drug exposure.

If pregnancy is confirmed in a patient during the course of the study, the patient must be taken off treatment and the pregnancy must immediately be recorded on the source documents and CRF, and will be reported by completing the Pregnancy Notification Form and emailing the form to the PI. Any pregnancy that occurs in a female partner of a male study participant will also be immediately recorded on the source documents and CRF and will be reported by completing the Pregnancy Notification Form and emailing the form to the PI. In addition, the Investigator must report to the Baylor IRB any follow-up information regarding the course of the pregnancy, including perinatal and neonatal outcome. Infants will be followed for a minimum of 8 weeks.

13 PROTOCOL AND DATA DEVELOPMENT

13.1 ETHICS

13.1.1 Institutional Review Board

This protocol will be implemented only after review and full approval of the protocol and the Patient Informed Consent Form has been obtained from a properly constituted IRB. This written approval must be dated and it must clearly identify the protocol, any amendments, the Patient Informed Consent Form, and any applicable recruiting materials and subject compensation programs approved.

During implementation of this protocol, the PI is required to send various documents to the IRB for review:

- 1. Changes to the current protocol.
- 2. All protocol amendments and Patient Informed Consent Form revisions.

3. Required progress reports.

Particular attention is drawn to the Food and Drug Administration (FDA) regulations regarding the IRB. The PI is responsible for the initial and continuing review and approval of the proposed clinical study in accordance with these regulations. At least once a year, the IRB will be asked to review and re-approve the tissue collection protocol; the request must be documented in writing. At the end of the trial, the PI will notify the IRB that the trial has been completed.

13.1.2 Patient Informed Consent

The informed consent should meet the requirements of the latest version of the Declaration of Helsinki and any applicable regulations and guidelines. It must be approved by an institutional ethics committee/IRB.

Prior to entry into the trial and before any protocol-required procedures are performed, the Investigator must explain the nature of the trial, its intended purpose, and the implications of participation to potential patients or to their legal representatives. They will be told about the possible risks and benefits, and the possible adverse experiences. They will be informed that patients' participation is voluntary, and that they may withdraw consent to participate at any time. They will also be informed that if patients choose not to participate in the trial, alternative treatments are available; such refusal will not prejudice further treatment of their disease. Potential patients or their legal representatives must be given the opportunity to ask questions about the trial protocol and the procedures involved.

Finally, each patient will be told that his or her records may be accessed by authorized personnel and other authorized individuals without violating the patient's confidentiality, to the extent permitted by the applicable laws and/or regulations. By signing the written Patient Informed Consent Form, the patient or his or her legal representative is authorizing such access. Following this explanation and prior to entry into the trial, the written, dated, and signed Patient Informed Consent Form must be obtained from each patient or his or her legal representative; a copy will be given to the person signing the form.

13.1.3 Confidentiality of Records

The Investigator is required to retain, in a confidential manner, sufficient information on each patient (eg, full name, current address, and social security number) so that the patient may be contacted by the FDA, should the need arise.

13.2 STUDY RECORDS

13.2.1 Documentation

A log of all patients evaluated for this protocol must be maintained. Patients excluded from admission will be provided with a clear explanation of the specific reasons why they have been excluded from the study. Patients who are included will be assigned a patient identification number.

For each patient treated with the study drug(s), the Research Coordinator is required to prepare and maintain case histories that include all observations and other data pertinent to the

investigation. This will include all source documents needed to verify the accuracy of all observations and other data contained in the CRFs on each study patient.

The Investigator or his/her designee is required to retain the records related to the trial for a period of 2 years following the date a marketing application is approved for the indication being investigated. If no application is to be filed or if the application is not approved for such indication, the records must be retained until 2 years after the investigation is discontinued and the regulatory agencies are notified.

13.2.2 Case Report Form Procedures

Data will be entered at the site using the protocol CRF. The Investigator or his/her designee is responsible for recording all data relating to the trial on the CRFs. The Investigator must verify that all data entries on the CRFs are accurate and correct. CRFs must be completed within 15 calendar days of the end of each cycle and within 15 calendar days following completion of study therapy.

13.3 MODIFICATION OF PROTOCOL

Any changes to this protocol that affect study objectives, study design, study procedures, patient population, or significant administrative procedures will require a formal amendment to the protocol. Any proposed protocol amendments must be sent in writing to the applicable IRB. Prior to implementation, an amendment must be agreed upon by the PI and approved by the IRB.

General administrative changes to the protocol are minor corrections and/or clarifications that do not affect the manner in which the study is to be conducted. Such administrative changes will be agreed upon by the PI and will be documented in a memorandum. The applicable IRB will be notified of administrative changes according to applicable IRB guidelines.

Appendix I NCI Common Terminology Criteria for Adverse Events (CTCAE), Version 4.0

Publish Date: May 28, 2009

COMMON TERMINOLOGY CRITERIA FOR ADVERSE EVENTS (CTCAE) Version 4.0

As of May 28, 2009 (v4.03: June 14, 2010), NCI has edited version 4.0 of the Common Terminology Criteria for Adverse Events. These may be obtained at the following web link http://ctep.cancer.gov/protocolDevelopment/electronic applications/ctc.htm.

Appendix II Schedule of Assessments

Assessment	Prestudy	During Treatment on Day 1 prior to each	End of	Follow-up every 3 months for 1
	As per 8.1	cycle, unless otherwise specified As per 8.2	Treatment up to 30±2 days following As per 8.3	year from the date of last treatment; research data only As per 8.4
Informed consent	~			•
Signed patient authorization (HIPAA)	~			
Inclusion/exclusion criteria	·			
Complete medical history	Within 4 weeks prior to registration (PTR)			
Complete physical examination (including vital signs, height, and body weight)	Within 4 weeks PTR			
Brief medical history		→	~	
Brief physical exam (vitals, weight)		✓	~	
Assessment of ECOG PS	Within 4 weeks PTR	→		
Assessment of conmeds	Within 4 weeks PTR	✓		
CBC with differential and platelet count	Within 4 weeks PTR	V 1	~	
Complete metabolic profile (CMP)	Within 4 weeks PTR	√ 1	~	
Mg and P	Within 4 weeks PTR	√ 1		
HbA1c	Within 4 weeks PTR	√ 1		
Fasting serum glucose	Within 4 weeks PTR	√ 1		
Serum pregnancy test	Within 7 days PTR		✓	
ECG	Within 4 weeks PTR	✓ 2		
Clinical assessment of disease	Within 4 weeks PTR	→	~	~
Radiological assessment of disease	Within 8 weeks PTR	As clinically indicated		As clinically indicated
Assessment of other lesions	Within 4 weeks PTR	To confirm CR		
Toxicity/AE		~	~	For 30 days following last dose
Research biopsies	Prior to the first day of treatment	After Cycle 2 or physician's discretion ³		
Whole blood (40 mL)	· .	After Cycle 2 or physician's discretion ³		
Patient diaries	✓	→	~	
Survival, relapse or PD, additional therapy 1 Day 1 and Day 15 of each 28-day cycle				~

¹ Day 1 and Day 15 of each 28-day cycle
² A pre-dose ECG (within 10 minutes of beginning prexasertib infusion) must be obtained on Cycle 1 and Cycle 2. A post-dose ECG (within 10 minutes of ending prexasertib infusion) must be obtained on Cycle 1 and Cycle 2. Additional ECG may be obtained if clinically indicated. **NOTE:** it is preferred to complete the postdose ECG upon completion of the prexasertib infusion, but prior to LY3023414 dosing.

³ Any time after the completion of Cycle 2 of the treatment combination, or at the physician's discretion.

